#### 7.2.2 Safety Profiles

#### 7.2.2.1 Nivolumab

Patients have received nivolumab at doses of 0.1, 0.3, 1, 3, 10, or 20 mg/kg intravenously every 2 weeks with no maximal tolerated dose identified[85]. The incidence, severity and relationship of AEs are generally similar across dose levels and tumor types. Nivolumab related AEs of any grade occur in approximately 75% of subjects[85]. The most frequently reported AEs are fatigue (54.9%), decreased appetite (35.0%), diarrhea (34.3%), nausea (30.1%), and cough (29.4%). Most treatmentrelated AEs are low grade. Treatment-related high grade (Grade 3-4) AEs have been reported in approximately. 17.0% of subjects. The most common treatment-related high grade AEs are fatigue (2.3%) and diarrhea (1%). Drug-related SAEs have been reported to occur in approximately in 11% of subjects. Select AE categories include: GI AEs, pulmonary AEs, renal AEs, hepatic AEs, skin AEs, and endocrinopathies. Patients who receive 10 mg/kg have had a numerically greater frequency of high-grade select AEs including the subcategories of endocrinopathies, GI, pulmonary, and infusion reaction. High grade events have been reported to resolve following the treatment guidelines for the treatment of pulmonary events, GI events, hepatic events, renal events, and endocrine events, respectively. Treatment-related AEs leading to discontinuation have been reported in 10.5%, the most frequent of these were pneumonitis (2.6%) and colitis (1.0%)[85].

#### 7.2.2.2 Pembrolizumab

The most common adverse reactions with Pembrolizumab include fatigue, pruritus, rash, constipation, diarrhea, nausea, and decreased appetite (Reported in >20% of patients) [86]. Pneumonitis has been reported to occur in approximately 2.9% of melanoma patients, including Grade 2 or 3 cases in 1.9% and 0.2% of patients, respectively [86]. The median time to development of pneumonitis was 5 months (range 0.3 weeks-9.9 months). The median duration was 4.9 months (range1 week-14.4 months). Five of eight patients with Grade 2 and one patient with Grade 3 pneumonitis required initial treatment with high-dose systemic corticosteroids followed by a corticosteroid taper. The median initial dose of high-dose corticosteroid treatment was 63.4 mg/day of prednisone or equivalent with a median duration of treatment of 3 days (range 1-34) followed by a corticosteroid taper. Pneumonitis led to discontinuation of Pembrolizumab in 3 (0.7%) patients. Pneumonitis completely resolved in seven of the nine patients with Grade 2-3 pneumonitis[86]. Colitis has been reported to occur in approximately 1% of patients, including Grade 2 or 3 cases in 0.2% and 0.5% of patients, respectively. The median time to onset of colitis was 6.5 months (range 2.3-9.8). The median duration was 2.6 months (range 0.6 weeks-3.6 months). All three patients with Grade 2 or 3 colitis were treated with high-dose corticosteroids with a median initial dose of 70 mg/day of prednisone or equivalent; the median duration of initial treatment was 7 days (range 4-41), followed by a corticosteroid taper. Hepatitis (including autoimmune hepatitis) has been reported to occur in approximately 0.5% of patients, including Grade 4 in 0.2% of patients. The time to onset was 22 days for the case of Grade 4 hepatitis which lasted 1.1 months. Hypophysitis has been reported to occur in approximately 0.5% of patients including Grade 2 and Grade 4 at at 0.2% each in patients. The time to onset was 1.7 months for the patient with Grade 4 hypophysitis and 1.3 months for the patient with Grade 2 hypophysitis. Hypophysitis may require permanent hormone replacement therapy. Nephritis has been reported to occur in approximately 0.7% of patients, including Grade 2 autoimmune nephritis (0.2%), and Grade 3 and Grade 4 interstitial nephritis with renal failure (0.5%). All patients fully recovered renal function with treatment with high-dose corticosteroids followed by a corticosteroid taper. Hyperthyroidism has been reported to occur in approximately 1.2% of patients, including Grade 2 or Grade 3 cases at 0.5% and 0.2% respectively. The median time to onset was 1.5 months (range 0.5-2.1). The median duration was 2.8 months (range 0.9 to 6.1). The following clinically significant, immune-mediated adverse reactions have been reported to occur in less than 1% of patients treated with Pembrolizumab: exfoliative dermatitis, uveitis, arthritis, myositis, pancreatitis, hemolytic anemia, partial seizures arising in a patient with inflammatory foci in brain parenchyma, adrenal insufficiency,

myasthenic syndrome, optic neuritis, and rhabdomyolysis.

#### 7.2.3 Nivolumab Dosing

Nivolumab will be dosed and scheduled according to FDA approved labels or per institutional guidelines at discretion of treating medical oncologist. For additional details regarding drug storage, preparation, and administration please refer to Nivolumab package insert[85]

#### 7.2.4 Nivolumab combined with Ipilimumab Dosing

Nivolumab combined with Ipilimumab will be dosed and scheduled according to FDA approved labels or per institutional guidelines at discretion of treating medical oncologist. For additional details regarding drug storage, preparation, and combination administration please refer to Nivolumab package insert[85]

#### 7.2.5 Pembrolizumab Dosing:

Pembrolizumab will be dosed and scheduled according to FDA approved labels or per institutional guidelines at discretion of treating medical oncologist. For additional details regarding drug storage, preparation, and combination administration please refer to Pembrolizumab package insert[86].

#### 7.2.6 Atezolizumab Dosing

Atezolizumab will be dosed and scheduled according to FDA approved labels or per institutional guidelines at discretion of treating medical oncologist. For additional details regarding drug storage, preparation, and administration please refer to Atezolizumab package insert [87]

#### 7.2.7 Avelumab Dosing

Avelumab will be dosed and scheduled according to FDA approved labels or per institutional guidelines at discretion of treating medical oncologist. For additional details regarding drug storage, preparation, and administration please refer to Avelumab package insert [88]

#### 7.2.8 Durvalumab Dosing

Durvalumab will be dosed and scheduled according to FDA approved labels or per institutional guidelines at discretion of treating medical oncologist. For additional details regarding drug storage, preparation, and administration please refer to Durvalumab package insert [89]

#### 7.2.9 Treatment of anti-PD-1/PD-L1 Related Infusion Reactions

Infusion reactions should be graded according to CTCAE Version 4.0 Allergic reaction/hypersensitivity criteria. Severe infusion reactions require the immediate interruption of anti-PD-1/PD-L1 therapy and permanent discontinuation from further treatment. Appropriate medical therapy including epinephrine, corticosteroids, intravenous antihistamines, bronchodilators, and oxygen should be available for use in the treatment of such reactions. Subjects should be carefully observed until the

complete resolution of all signs and symptoms. In each case of an infusion reaction, the investigator should institute treatment measures according to the best available medical practice.

# 8 DOSING DELAYS/DOSE MODIFICATIONS AND DISCONTINUATION CRITERION

#### 8.1) Dose Delay Criterion for CBI or CBI combined with SBRT

Dose delay criteria specified below apply for all checkpoint blockade immunotherapies or any combination of checkpoint blockade immunotherapies with SBRT (regardless of whether or not the event is attributed to CBI, SBRT or both)

CBI and SBRT administration should be delayed for the following:

- Any Grade  $\geq 2$  non-skin, drug-related adverse event, with the following exceptions:
  - Grade 2 drug-related fatigue or laboratory abnormalities do not require a treatment delay
- Any Grade 3 skin, drug-related adverse event
- Any Grade 3 drug-related laboratory abnormality, with the following exceptions for asymptomatic amylase or lipase, AST, ALT, or total bilirubin:
  - Grade 3 amylase or lipase abnormalities that are not associated with symptoms or clinical manifestations of pancreatitis do not require a dose delay.
  - If a subject has a baseline AST, ALT, or total bilirubin that is within normal limits, delay dosing for drug-related Grade  $\geq 2$  toxicity
  - If a subject has baseline AST, ALT, or total bilirubin within the Grade 1 toxicity range, delay dosing for drug-related Grade  $\geq$  3 toxicity
- Any adverse event, laboratory abnormality, or concurrent illness which, in the judgment of the investigator, warrants delaying the dose of study medication.

#### 8.2) Discontinuation Criterion for CBI or CBI combined with SBRT:

Discontinuation criteria apply for all drug-related adverse events attributed to checkpoint blockade immunotherapies or any combination of checkpoint blockade immunotherapies with SBRT (regardless of whether or not the event is attributed to CBI, SBRT or both)

Treatment should be permanently discontinued for the following:

- Any Grade 2 drug-related uveitis, eye pain, or blurred vision that does not respond to topical therapy and does not improve to Grade 1 severity within the re-treatment period OR requires systemic treatment.
- Any Grade 3 non-skin, drug-related adverse event lasting > 7 days, with the following exceptions for drug-related laboratory abnormalities, uveitis, pneumonitis, bronchospasm, diarrhea, colitis, neurologic toxicity, hypersensitivity reactions, and infusion reactions:
  - Grade 3 drug-related uveitis, pneumonitis, bronchospasm, diarrhea, colitis, neurologic toxicity, hypersensitivity reaction, or infusion reaction of any duration requires discontinuation

o Grade 3 drug-related laboratory abnormalities do not require treatment discontinuation except: ☐Grade 3 drug-related thrombocytopenia > 7 days or associated with bleeding requires discontinuation

Any drug-related liver function test (LFT) abnormality that meets the following criteria require discontinuation:

- $\circ$  AST or ALT  $> 8 \times ULN$
- Total bilirubin > 5 x ULN
- Concurrent AST or ALT > 3 x ULN and total bilirubin > 2 x ULN
- Any Grade 4 drug-related adverse event or laboratory abnormality, except for the following events which do not require discontinuation:
  - Grade 4 amylase or lipase abnormalities that are not associated with symptoms or clinical manifestations, or radiographic signs of pancreatitis.
  - Isolated Grade 4 electrolyte imbalances/abnormalities that are not associated with clinical sequelae and are corrected with supplementation/appropriate management within 72 hours of their onset.

If a subject discontinues combination CBI treatment for example with nivolumab + ipilimumab due to a drug-related adverse event prior to completing four doses of the combination therapy, the subject may continue treatment with nivolumab 3mg/kg every 2 weeks as long as the AE leading to discontinuation was clearly attributed to ipilimumab and not nivolumab. In such circumstances, the subject may re-start nivolumab therapy when the subject fully recovers from the drug-related adverse event that led to discontinuation.

#### 8.3) Dose Modification for SBRT:

Dose modifications to SBRT due to safety or toxicity concerns will be performed by the treating radiation oncologist as clinically indicated. This includes dose reduction below 9.5Gy x3 fractions in order to meet tolerances listed above for critical normal structures when deemed necessary by the treating radiation oncologist. The minimum dose of SBRT delivered will be 6Gy x3 fractions.

## 9 **CORRELATIVE/SPECIAL STUDIES**

#### 9.1) Blood Sample Transport, Processing, and Storage.

- 9.1.1 A peripheral blood draw (80cc maximum for adults and 20 cc maximum for participants <18 years old or those under a specific weight criteria) will be obtained by venipuncture in BD Vacutainer® CPTTM (Franklin Lakes, NJ) tubes or an appropriate substitute cell preparation tube at baseline prior to treatment, prior to cycle #2 of CBI, and at 2 month post-SBRT follow-up visit.
- 9.1.2 The study coordinator or research staff from the laboratory of [name] will transport the specimen to the laboratory of [name]., PhD for storage and processing. Samples will be stored indefinitely.
- 9.1.3 Blood for serum should be collected in standard 10 ml red top polypropylene tubes and allowed to clot for 30 minutes at room temperature in a vertical position. The

- samples should be separated in a centrifuge for 30 minutes at 3500 rpm. Without delay, 1.5 ml serum aliquots should be pipetted into a 2.0 ml snap cap cryovials. After removing the serum, the red top tube will be discarded and each cryovial will be labled with the date and patient case ID to protect patient privacy. Cyrovials will be frozen immediately at -70°C in a dedicated freezer in the laboratory of [name]. If a -70°C freezer is not available serum samples may be stored at -20°C..
- Blood for plasma should be collected in standard 10 ml Heparin coated tubes. The 9.1.4 samples should be immediately separated in a centrifuge for 10 minutes at 1500 +/-150g (=1500RCF). Without delay, transfer the resulting supernatant plasma to a fresh 15 ml conical centrifuge tube. After removing the plasma, use the same transfer pipet to carefully aspirate the exposed WBC layer (buffy coat) in a volume of 1 ml or less. Aspirate slowly, using a circular motion, to pull all the visible buffy coat material into the pipet. Expel the buffy coat into one cryovial. Discard the lavender top tubes and the transfer pipet tip. Label each buffy coat cryovial with the with the date and patient case ID to protect patient privacy. Run the 15 ml conical centrifuge tube containing the supernatant plasma in a centrifuge for a second time for 10 minutes at 1500 +/- 150g (=1500RCF). Without delay and using a fresh transfer pipet tip, 1.5 ml plasma aliquots of the resulting supernatant should be pipetted into a 2.0 ml snap cap cryovials. Leave a residual volume of about 0.3 ml (~7 mm) on the bottom of the 15 ml conical centrifuge tube to avoid cellular contamination. Cyrovials will be frozen immediately at -70°C in a dedicated freezer in the laboratory of [name]. If a -70°C freezer is not available serum samples may be stored at -20°C.

#### 9.2) Assessment of Immune Reponses

- 9.2.9 Multiparametic Flow cytometery will be used to analyze Immune subset proportions (%CD4+ T-cells, %CD8+ T-cells, %Treg T-cells, %Myeloid Derived Suppressor Cells, %Natural Killer cells, etc.) will be determined by flow cytometry analysis performed in the UCSD Moores Cancer Center Flow Cytometry Core.
- 9.2.10 T-cell Receptor Repertoire analysis will be performed on Baseline and post-treatment PBMC. DNA will be extracted and assessed for quality control utilizing standard manufacturer DNA extraction kits and per manufacturer instructions (i.e. DNeasy, Qiagen, N.V.) and per standard spectrophotometric 260nm/280nm methods. Extracted DNA from each sample will be analyzed for T-cell and B-cell receptor mutations by next generation sequencing on the Adaptive Biotechnologies Immunoseq platform. This work will be outsourced and performed in collaboration with Adaptive Biotechnologies (Seattle, WA).
- 9.2.11 Sequencing Analysis. DNA will be extracted and assessed for quality control utilizing standard manufacturer DNA extraction kits and per manufacturer instructions (i.e. DNeasy, Qiagen, N.V.) and per standard spectrophotometric 260nm/280nm methods. Extracted DNA from each sample will be analyzed for overall mutation burden, individual gene mutations, and individual gene fusions on the Illumina HiSeq Next Generation Sequencing platform.
- 9.2.12 Serum markers and cytokine of interest (i.e. IFN- TGF- IL-10, IL-4, IL-5, IL-

- 13, IFN- will be analyzed will be selected based on assay methodology optimization and validation testing.
- 9.2.13 Additional exploratory analysis of the relationship between circulating free tumor DNA/RNA, micro-RNA, and other novel platforms will be pursued as resources and specimen availability permit.

# 10 STUDY CALENDAR

Parameter	Dro	CBI	SBRT	CBI	CBI	Post			Post	Post	Post C1D1
	- AT	Cycle#1 3 Fx	3 Fx	Cycle #2	Cycle#3+	C1D1	C1D1	C1D1	C1D1	C1D1	24mo @
	Y					8 weeks	8 weeks 16 weeks 6mo @ 12mo @ 18mo @	6mo (a)	12mo @	18mo @	
						(a)	(a)				
Informed Consent	X										
Demographics	X										
Med HX & Medication Rev	×					×	×	×	×	×	×
Physical Exam	×					×	×	×	×	×	×
Standard of Care Labs	×	×		×	×	×	×	×	×	×	×
Research Blood Draw	*X			*X		× *					
Imaging Assessment	X					X	×		×	×	×
AE Evaluation	X	×		×	×	×	×	×	×	×	×

 $\sim$  SBRT: to be administered in three fractions. \* indicates optional @ +/- 10 days

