#### **6.3** Follow-Up Procedures

Subsequent to Cycle 1 Day 1, patients will be followed clinically, radiographically, and with bloodwork. A detailed medical and physical examination will be performed at 8 weeks and 16 weeks, 6 months, 12 months, 18 months and 24 months. A complete blood count (CBC) and comprehensive chemistry panel and CT scan including the treated site will be performed at the 8 week and 16 week follow-up and will continue at intervals of every 6 months until 2 years post SBRT treatment.

Tumor measurements (Recist 1.1) at 8 weeks (+/- 10 days) and 16 weeks (+/- 10 days) will be used to determine radiographic response.

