#### 11 MEASUREMENT OF EFFECT

#### 11.1 Antitumor Effect-Solid Tumors

For the purposes of this study, patients should be re-evaluated for response 8 weeks after the initial treatment, 16 weeks after treatment, and at 6 month intervals thereafter.

Response and progression will be evaluated in this study using the new international criteria proposed by the Response Evaluation Criteria in Solid Tumors (RECIST 1.1) Committee (30). Changes in only the largest diameter (unidimensional measurement) of the tumor lesions are used in the RECIST criteria.

The RECIST read at 16 weeks will be used to determine the objective response rate for the primary endpoint of this study.

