#### 11.5.3 Duration of Response

Response will be defined as evidence of CR, PR, or stable disease. The duration of response will be measured from the start of treatment until the criteria for progression are met.

Duration of CR or PR: The duration of CR or PR will be recorded from the time measurement criteria are met for CR or PR (whichever is first recorded) until the first date that current or progressive disease is objectively documented (taking as reference for progressive disease the smallest measurements recorded since the treatment started).

Duration of Stable Disease: Stable disease is measured from the start of the treatment and must be at least 6 months in duration or until the criteria for progression are met, taking as reference the smallest measurements recorded since the treatment started.

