#### 15.1.2 Secondary Objectives

- To assess the safety and toxicity of CBI used concurrently with SBRT delivered in the population enrolled using grading with CTCAE v. 4.0
- O To assess progression free survival and overall survival in patients after completion of SBRT in combination with CBI. Progression-free survival will be measured from time of enrollment to date of disease progression or death. Patients who are lost to follow-up will be censored for determination of progression-free survival on the date of their last evaluation. Overall survival is defined as time from enrollment to death

due to any cause.

- o To assess the rates of stable disease great than or equal to 6 months during and after SBRT in combination with CBI compared to CBI alone
- o To determine whether SBRT combined with concurrent CBI results improvements in anti-tumor immune responses compared to CBI alone

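### The calendar leaves 6-month imaging blank, against 6.3; if it is followed, stable disease of at least 6 months and median PFS are coarse and biased upward

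*Combined protocol and SAP*

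**What the plan says.** Three places set the imaging schedule.

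- **Section 10, Study Calendar.** The row "Imaging Assessment" has marks at baseline, 8 weeks, 16 weeks, 12, 18 and 24 months. Its 6-month cell is empty. The rows for medical history, physical exam, laboratory tests and AE evaluation all carry a mark at 6 months. Post-treatment columns are counted from C1D1, and the footnote ("indicates optional @ +/- 10 days") gives a window of 10 days either side.
- **Section 6.3.** Visits are listed first: "A detailed medical and physical examination will be performed at 8 weeks and 16 weeks, 6 months, 12 months, 18 months and 24 months". The next sentence puts blood count, chemistry and CT on one schedule, at 8 and 16 weeks, which "will continue at intervals of every 6 months until 2 years post SBRT treatment".
- **Section 11.1.** Response is re-evaluated at 8 weeks, then "16 weeks after treatment, and at 6 month intervals thereafter".

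The outcomes that depend on later scans are secondary. Section 15.1.2 states the aim "To assess the rates of stable disease great than or equal to 6 months during and after SBRT", compared between the arms. Section 11.5.3 adds: "Stable disease is measured from the start of the treatment and must be at least 6 months in duration". Section 11.5.4 makes the first documented progression or death the PFS event, and section 15.6 reports median PFS and median SD. The primary endpoint is fixed earlier, in section 11.1: "The RECIST read at 16 weeks will be used to determine the objective response rate".

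**The concern.** The calendar is the page that sites schedule from. Followed as it stands, it requires no scan between week 16 and month 12, although one secondary endpoint is defined by a threshold at month 6. A patient who progresses radiographically in month 5, without an unscheduled scan, is first found to have progressed at month 12. Dated at that scan, the patient counts as stable for at least 6 months, and the PFS time is far too long. The censoring rule adds to this: section 11.5.4 censors PFS at the last visit, so a patient last seen at a 6-month visit without a scan is credited with 6 progression-free months that no image supports. At stake are the interpretation of the stable-disease rate and of the PFS curve in both arms.

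**Working it through.** The plan states no figure that depends on the scan schedule, so there is none to reproduce. The check has three steps.

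**1. Is the blank cell misaligned?** The exam, laboratory, imaging and AE rows each have 12 cells (one label and 11 time points). In the 6-month position exam, laboratory and AE are marked and imaging is not. Section 6.3 schedules laboratory tests and CT together; the calendar marks the first at 6 months and not the second.

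**2. Length of the gap.** One month = 365.25/12 = 30.44 days. Week 16 = 112/30.44 = 3.68 months.

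| Source | Next scan after week 16 | Gap |
|---|---|---|
| Calendar | month 12 | 12 − 3.68 = 8.32 months (36 weeks) |
| 6.3, read on its visit grid | month 6 | 6 − 3.68 = 2.32 months (10 weeks) |
| 11.1, read literally | 3.68 + 6 = month 9.68 | 6.00 months |

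**3. Size of the distortion.** The documents give no median PFS, so the median m is an assumption, taken from 4 to 12 months. Further assumptions are exponential progression, S(t) = 0.5^(t/m), no deaths, no off-schedule scans, and each progression dated at the scan that finds it. With no scan between week 16 and month 6, the apparent progression-free share at month 6 is simply S(3.68). The true share is S(6).

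- m = 4: apparent 0.5^(3.68/4) = 0.529; true 0.5^(6/4) = 0.354.
- m = 6: apparent 0.5^(3.68/6) = 0.654; true 0.5^(6/6) = 0.500.

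| Assumed m (months) | True share at 6 months | Apparent share | Excess (points) | Progress between week 16 and month 12, all patients | Same, of those progression-free at week 16 |
|---|---|---|---|---|---|
| 4 | 35.4% | 52.9% | 17.5 | 40% | 76% |
| 6 | 50.0% | 65.4% | 15.4 | 40% | 62% |
| 8 | 59.5% | 72.7% | 13.2 | 37% | 51% |
| 12 | 70.7% | 80.9% | 10.1 (from unrounded shares) | 31% | 38% |

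The fifth column is S(3.68) − S(12); the sixth divides it by S(3.68). The literal reading of 11.1 also has no scan between 3.68 and 6 months, so its apparent share at month 6 is the same as the calendar's.

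The scan-dated median is the first scan time at which S(t) is 0.5 or less. Under the calendar it is 12 months for every assumed median from 4 to 12. With a month-6 scan it is 6 months for true medians of 4 to 6, and 12 months for true medians of 8 to 12: still coarse, but no longer the same value throughout.

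**The case against.** The strongest case on the other side has five parts.

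- **The blank may be a lost mark.** The calendar's header is garbled in the copy read, and equal cell counts do not prove that a cell was always empty. This cannot be fully excluded, and the original page should be checked. If a mark is there, calendar and 6.3 agree and only 11.1 needs aligning.
- **Section 6.3 already provides the scan.** On its natural reading it does, although it does not name a 6-month CT. The problem is therefore a contradiction between passages, and harm follows only if sites work from the calendar or from the literal 11.1.
- **Sections 6.3 and 11.1 could be read alike**, as the same 6, 12, 18 and 24-month grid. That is possible, but the wording of 11.1 counts from week 16, and a site could follow it literally.
- **The figures are an upper bound on a related quantity.** This stands. Deaths and unscheduled scans would shrink the excess. The progression-free share also includes complete and partial responders, whereas the endpoint is a stable-disease rate; with planning response rates of 20% to 61% in section 15.2 the two can differ widely.
- **The post-SBRT end date is minor.** This also stands. Section 6.3 opens by counting from Cycle 1 Day 1, and SBRT falls within 21 days of Cycle 1, so the end date moves by about three weeks at most. Control patients nevertheless have no SBRT date.

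A reader might infer that stable disease of at least 6 months and PFS cannot be measured at all. The documents do not support that. Progression by week 16 is detected, a patient still stable at month 12 clearly passed 6 months, deaths are PFS events on their own date, and any documented off-schedule progression counts. A reader might also infer a bias in the comparison between arms. Both arms share the calendar, and only the inflation within an arm has been shown here.

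**Conclusion.** The point holds as an internal contradiction with a real consequence for secondary endpoints. If the calendar is followed, progression between month 3.7 and month 12 is interval-censored, and the stable-disease rate at 6 months and median PFS are coarse and biased upward. As an upper bound, for assumed medians of 4 to 6 months, the progression-free share at month 6 reads 53% to 65% instead of 35% to 50%; over medians of 4 to 12 months the excess is 10 to 18 points. These sizes rest on the assumptions in the working, none of which the documents supply. The 16-week objective response rate and the sample size are untouched. The inconsistency should be corrected, but it does not threaten the main result.

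**What to change.** Reconcile the three passages to one imaging schedule, counted from C1D1 in both arms:

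1. In the calendar, mark imaging at the existing 6-month visit (+/- 10 days), in line with 6.3.
2. In 11.1, list the assessments as 8 weeks, 16 weeks, then 6, 12, 18 and 24 months.
3. In 6.3, end scheduled imaging 2 years from C1D1 in place of 2 years after SBRT.

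Because the window around month 6 runs 10 days either way, 11.5.3 should also say how progression found at the 6-month scan counts toward the 6-month threshold.

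The scan-free gap after week 16 then falls from 8.3 to 2.3 months. No visit is added. If the calendar reflected the intent, the cost is one more scan for each patient still in follow-up at month 6, about 10 weeks after the week-16 scan and charged to patients or insurers under section 6.8. On its natural reading, 6.3 already asks for that scan.
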